### 3.4 Definition of dose-limiting toxicity (DLT)

DLT is defined as clinically significant non-hematologic adverse event or abnormal laboratory value assessed as unrelated to disease progression, intercurrent illness, or concomitant medications and occurring during the first cycle on study and at least possibly related to the study drugs that meets any of the following criteria:

- CTCAE Grade 3 AST (SGOT) or ALT (SGPT) for  $\geq 7$  days
- CTCAE Grade 4 AST (SGOT) or ALT (SGPT) of any duration
- Grade 3 nausea/vomiting, dehydration or diarrhea lasting more than 3 days in the setting of optimal supportive medications
- Grade 3 fatigue lasting more than 5 days in the setting of optimal supportive medications
- Grade 3 biochemical abnormalities (e.g., lipase or bilirubin elevation) will only be considered DLT if accompanied by clinical consequences. Grade 3 electrolyte abnormalities will only be considered DLT if possibly related to study drug and not corrected by optimal replacement therapy or if the Grade 3 electrolyte abnormalities persist after 7 days of optimal replacement therapy
- All Grade 4 non-hematologic toxicities of any duration
- For the purposes of DLT assessment, asymptomatic hyponatremia will be “graded” not by the NCI CTCAE version 4.03 but rather by clinically meaningful criterion of  $<125\text{mmol/L}$ . Sodium  $<125\text{mmol/L}$  will be graded as DLT with the exception of asymptomatic translational hyponatremia due to hyperglycemia (see footnote below for calculation).  
*\*In marked hyperglycemia, ECF osmolality rises and exceeds that of ICF, since glucose penetrates cell membranes slowly in the absence of insulin, resulting in movement of water out of cells into the ECF. Serum Na concentration falls in proportion to the dilution of the ECF, declining 1.6 mEq/L for every 100 mg/dL (5.55 mmol/L) increment in*

*the plasma glucose level above normal. This condition has been called translational hyponatremia because no net change in total body water (TBW) has occurred. No specific therapy is indicated, because Na concentration will return to normal once the plasma glucose concentration is lowered. Corrected Sodium (Hillier, 1999) = Measured sodium + 0.024 \* (Serum glucose - 100).*

- All other clinically significant non-hematological adverse event that is Grade 3 according to the NCI CTCAE version 4.03.

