- Myelosuppression and cytopenias are expected outcomes of leukemia treatment and per se will not constitute DLT. Only prolonged myelosuppression, as defined by the NCI criteria specific for leukemia, i.e. marrow cellularity < 5% on Day 42 or later (6 weeks) from start of therapy without any evidence of leukemia, will be considered in defining DLT. In case of a normocellular bone marrow with <5% blasts, 8 weeks with pancytopenia will be considered DLT. Anemia will not be considered for the definition of DLT.

Any patients who stop treatment prior to completing evaluation for the DLT observation period (first 28 days) due to disease progression or refusal for further participation for reasons other than toxicity during the DLT defining phase I portion of the study will be replaced at that dose level for a full evaluation of that dose level before a decision regarding dose escalation can be made.

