**5.1.1.5** Patients must receive at least 4 doses of selinexor and at least 44 doses of sorafenib during the first 28 days on trial (i.e. during cycle 1) to be evaluated for DLT. Patients who receive less than 4 doses of selinexor and/or less than 44 doses of sorafenib during the first 28 days on trial will not be evaluable for DLT. Patients not evaluable for DLT will be replaced. These patients may continue therapy on trial

after discussion with the PI if they are having clinical benefit and the reasons for continuation and potential benefit/risk profile for the patient must be clearly documented in the medical records.

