**Table 4 Dose adjustments for non-hematologic drug-related AEs, clinically significant in the opinion of the investigator**

Grade	Occurrence	Dose modification
1 or 2	Any time	No dose reduction.
3  (Persistent grade 2: Consider	1st and 2nd time	Hold selinexor and/or sorafenib. Resume selinexor and/or sorafenib at prior dose if recovery to $\leq$ Grade 1 or baseline occurs within 14 days. If toxicity persists for 15-28 days, hold therapy and resume at ONE dose level below current dose for selinexor OR sorafenib

similar dose adjustments if persistent and not responding to optimal management in the opinion of PI and treating physician)		OR both based on which medication is likely causing the toxicity ONLY after recovery of toxicity to $\leq$ Grade 2. Dose re-escalation to prior dose of selinexor OR sorafenib OR both is permitted if tolerated and no recurrent Grade 3 or 4 toxicities occur over 4 weeks while on the lower dose level.
	3 rd and 4th time	Hold selinexor and/or sorafenib. Follow until toxicity $\leq$ Grade 2. Resume at TWO dose level below current dose for selinexor OR sorafenib OR both based on which medication is likely causing the toxicity ONLY after recovery of toxicity to $\leq$ Grade 2. Dose re-escalation by one dose level every 4 weeks of selinexor OR sorafenib OR both is permitted if tolerated and no recurrent Grade 3 or 4 toxicities occur over the 4 weeks while on the lower dose level.
	5th time	Stop selinexor and sorafenib and discontinue patient. (For patients with clinical benefit/response from the combination we will consider continuation if toxicities resolve to $\leq$ grade 1 and with proper dose adjustments after consultation with the PI and the sponsor)
4	Any time	Stop selinexor and sorafenib and discontinue patient. (For patients with clinical benefit/response from the combination we will consider continuation if toxicities resolve to $\leq$ grade 1 and with proper dose adjustments after consultation with the PI and the sponsor)

- If the criteria to resume treatment are met, the subject should restart treatment at the next scheduled time point per protocol. However, if the treatment is delayed past the next scheduled time point per protocol, the next scheduled time point will be delayed until dosing resumes.

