### 11.1 Phase I

In order to determine the MTD of selinexor in combination with sorafenib, we will use the standard 3+3 design for dose finding. The MTD is defined as the highest dose level with  $\leq 1$  out of 6 patients experience a DLT during the first 28 days of treatment. **DLT is defined in section 3.4 (page 13)**. The 3+3-dosing algorithm is presented in section 3.3 and the dosing schema for the combination treatment is shown in Table 3. The RP2D will be selected at the end of the phase I portion based on safety and efficacy of selinexor and sorafenib after discussion with the sponsor and the supporting company (Karyopharm). The Investigator is responsible for completing the cohort summary template prior to advancing subjects to the phase II part. Once RP2D has been established, any patients

still on study at a dose lower than RP2D can be dose escalated up to RP2D in accordance with the dose-escalation guidelines in section 5.2.3.

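### The DLT-evaluability rule removes and replaces patients who missed doses because of a DLT, so the 3+3 count is too low and the MTD is biased upward

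*Combined protocol and SAP*

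**What the plan says.** Section 5.1.1.5 sets the minimum exposure: "Patients must receive at least 4 doses of selinexor and at least 44 doses of sorafenib during the first 28 days on trial". It then states the consequence without conditions. "Patients who receive less than 4 doses of selinexor and/or less than 44 doses of sorafenib during the first 28 days on trial" are not evaluable, and "Patients not evaluable for DLT will be replaced". The reason for the missed doses plays no part.

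Section 3.4 has its own replacement rule. It replaces patients who stop before the end of the 28-day observation period "due to disease progression or refusal for further participation for reasons other than toxicity". By implication, someone who stops for toxicity is not replaced, but 3.4 does not say that such a patient is counted. It is also silent on patients whose doses were held rather than stopped.

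The DLT list in 3.4 includes "CTCAE Grade 3 AST (SGOT) or ALT (SGPT) for" at least 7 days, and every grade 4 non-haematologic toxicity. Table 4 calls for one or both drugs to be held for a grade 3 drug-related event. For grade 4 it reads "Stop selinexor and sorafenib and discontinue patient", with continuation considered for patients who benefit.

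On the window, 3.4 confines DLTs to the first cycle, and 11.1 defines the MTD by patients who "experience a DLT during the first 28 days of treatment". The prolonged-myelosuppression criterion in 3.4, however, requires a hypocellular marrow "on Day 42 or later (6 weeks) from start of therapy", or 8 weeks of pancytopenia with a normocellular marrow.

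**The concern.** A minimum-exposure rule is meant to stop an under-dosed patient without a DLT from being counted as evidence that the dose is tolerable. Applied to patients with a DLT it does the reverse: the event interrupts treatment, the interruption makes the patient non-evaluable, and a replacement without the event may take the slot. Exclusion then depends on the outcome being counted.

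The MTD and RP2D are the phase I primary objective. Each decision rests on 3 to 6 patients, so one lost DLT can turn a failed level into a cleared one. The selected dose then goes to as many as 40 phase II patients (20 per cohort).

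The haematologic criterion loses DLTs by a separate route: it needs at least 42 days to be met, but only the first 28 are counted.

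**Working it through.** The documents give no target DLT rate and no operating characteristics for phase I, so there is no figure of the plan's own to reproduce.

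**Step 1. Doses planned and doses that may be missed (5.1.1, Table 3, 5.1.1.5)**

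- Sorafenib: 2 per day × 28 days = 56. Minimum 44, so at most 56 − 44 = 12 may be missed, which is 6 days.
- Selinexor: 2 per week × 3 weeks = 6. Minimum 4, so at most 2 may be missed.

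**Step 2. DLTs that fall below the minimum**

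- Grade 3 AST/ALT lasting 7 days, sorafenib held for those 7 days within the 28: 56 − 14 = 42 < 44. Not evaluable.
- Grade 4 event with both drugs stopped before the day-d doses: 2(d − 1) sorafenib doses taken. At d = 22 this is 42. Every such stop on or before day 22 makes the patient non-evaluable.
- Selinexor on days 1, 3, 8, 10, 15 and 17: stopping after day 3 leaves 2 doses and stopping after day 8 leaves 3. A 14-day hold that starts on any of days 1 to 10 misses 3 or 4 doses. All are below the minimum.

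**Step 3. Effect on the 3+3 decision**

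Let p be the true DLT rate and f the share of DLT patients who fall below the minimum and are replaced. Both are assumptions. Among patients still counted, the DLT rate is

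q = p(1 − f) / (1 − pf).

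Under 3.3 a level clears with 0 of 3, or with 1 of 3 and then 0 of 3:

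P(clear) = (1 − q)³ + 3q(1 − q)² × (1 − q)³.

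Example with p = 0.40 and f = 0.5: q = 0.40 × 0.5 / (1 − 0.20) = 0.25. P(clear) = 0.75³ + 3 × 0.25 × 0.75⁵ = 0.422 + 0.178 = 0.600.

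| True rate p | f = 0 | f = 0.25 | f = 0.5 | f = 0.75 |
|---|---|---|---|---|
| 0.30 | 49% | 61% | 76% | 91% |
| 0.33 | 43% | 56% | 71% | 89% |
| 0.40 | 31% | 43% | 60% | 83% |
| 0.50 | 17% | 26% | 43% | 71% |

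Section 3.3 defines the MTD more strictly, as a level with six patients treated and at most one DLT. The chance of at most 1 DLT in 6 at p = 0.40 is 23%, 35%, 53% and 79% for the same values of f.

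**Step 4. Whole algorithm**

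The 3.3 algorithm was simulated from level 0 (100,000 trials for each value of f), with assumed DLT rates of 10%, 15%, 25% and 45% at levels −2, −1, 0 and +1.

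| | f = 0 | f = 0.25 | f = 0.5 | f = 0.75 |
|---|---|---|---|---|
| P(MTD = level +1) | 9.8% | 18.8% | 36.6% | 68.6% |
| Mean true DLT rate at declared MTD | 22.0% | 25.3% | 30.3% | 38.1% |

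**Step 5. Haematologic criterion**

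The earliest it can be met is Day 42, which is 14 days after the 28-day window closes. The other form needs 8 × 7 = 56 days. Under the 11.1 definition neither can enter the count.

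**The case against.** The strongest reply is that 3.4, which 11.1 cites for the DLT definition, does not list toxicity among its reasons for replacement, so the authors presumably meant such patients to count. That is probably the intent, but it is only implied. It does not cover held doses, and it cannot be squared with the unconditional wording of 5.1.1.5. A team that follows 5.1.1.5 literally drops these DLTs.

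The remaining objections concern size, and they stand to that extent:

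- **Not every DLT is lost.** Table 4 allows only one drug to be held, and 5.1.1.3 lets the other continue. A sorafenib hold that starts on day 23 or later misses at most 12 doses. A selinexor-only hold of up to 7 days misses at most 2 doses. In these cases the patient still counts.
- **Table 5 differs from Table 4.** For several selinexor-related grade 4 events it interrupts or delays and then reduces, where Table 4 discontinues. How often patients fall short depends on which table is followed, and the two must be reconciled.
- **f has no source in the documents.** At f = 0.1 and p = 0.40 the chance of clearing is only 35%, against 31%. The limiting case f = 1 is not realistic, because late DLTs are counted.
- **There are later safeguards.** The medical monitor approves each cohort summary (3.2), RP2D selection considers safety (3.5), one dose of either drug makes a patient evaluable for general toxicity (5.3.2), and phase II has toxicity stopping rules. None of these is a counting rule for DLTs. The phase II rules are a partial backstop: from the boundaries in Tables 7 and 10, toxicity alone would stop a cohort with probability 27% and 47% at a true toxicity rate of 40%, and 56% and 75% at 50%. They also use a different endpoint from DLT.

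The haematologic window is a separate mechanism and adds nothing to the figures above. It belongs here because it affects the same count.

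**Conclusion.** The concern holds. As written, 5.1.1.5 excludes and replaces patients because of the event the design is meant to count, and no other section overrides it. The bias is upward for any f above 0. Its size depends on p and f, which the documents do not give. At a true DLT rate of 40%, losing a quarter to three quarters of DLT patients raises the chance of clearing a level from 31% to between 43% and 83%. On the six-patient MTD criterion it rises from 23% to between 35% and 79%. Separately, the haematologic criterion cannot be met within the 28 days in which DLTs are counted. Both faults bear on the phase I primary objective and should be corrected before the DLT count is used.

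**What to change.** Add to 5.1.1.5: *A patient who has a DLT is evaluable and is counted, whatever number of doses was received. The minimum of 4 selinexor and 44 sorafenib doses applies only to patients without a DLT.* Limit the replacement sentence in 5.1.1.5 to patients without a DLT, make the replacement rule in 3.4 say the same, and use this one definition of DLT-evaluable in 3.3, 3.4, 5.1.1.5 and 11.1.

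Reconcile the 28-day counting window in 3.4 and 11.1 with the Day-42 and 8-week haematologic criterion, so that the criterion can enter the count. Reconcile the grade 4 actions in Tables 4 and 5. Which clinical rule should prevail is for the investigator and sponsor.

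The evaluability change costs one sentence and some alignment of wording. It alters no dose, adds no patients and reduces the number of replacements. The window needs a short protocol clarification.

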## 5.2 Dose Adjustments

### 5.2.1 Selinexor and sorafenib dose adjustments for drug-related hematological adverse events (AEs):

Dose reduction/interruption/discontinuation decisions should be based on the CTCAE version 4.03 (Appendix E) of the toxicity and the guidelines provided below.

- Patients with acute leukemia's usually present with abnormal peripheral blood counts at the time therapy is started and myelosuppression is an expected event during the course of therapy for acute leukemia's. Thus, no dose adjustments or treatment interruptions for myelosuppression will be planned for the first 4 cycles and/or in the presence of residual leukemia. After that, treatment interruptions and dose adjustments may be considered according to the following guidelines only when there is no evidence of residual leukemia.
  - Patients with a response (e.g., no evidence of residual leukemia or cytopenias not considered to be related to leukemia) and pre-cycle counts of neutrophils  $>1.0 \times 10^9/L$  and platelets  $>50 \times 10^9/L$  who have sustained low counts of neutrophils  $<0.5 \times 10^9/L$  or a platelet count  $<20 \times 10^9/L$  for more than 2 consecutive weeks in the current cycle, may have the treatment with selinexor and sorafenib interrupted at the discretion of the treating physician after discussing with the PI until neutrophils recover to  $\geq 0.5 \times 10^9/L$  and platelets to  $\geq 30 \times 10^9/L$ . If prolonged myelosuppression defined as  $ANC < 0.5 \times 10^9/L$  and platelets  $< 20 \times 10^9/L$  (more than 8 weeks) with evidence of a hypocellular marrow (marrow cellularity less than 5% without evidence of leukemia) is observed in these patients, both selinexor and sorafenib will be discontinued. Delays in start of subsequent cycles greater than 8 weeks will be acceptable only for patients who are deriving clinical benefit and after discussion with the principal investigator of potential risk/benefit ratio and complete documentation of the degree of clinical benefit and reason for continuation on this regimen.

- If there are persistent peripheral blood blasts, or the bone marrow shows >5% blasts or evidence of leukemia, treatment may be continued regardless of neutrophil and platelet count with supportive care as needed. Dose-interruptions of selinexor and sorafenib in these patients should be considered on an individual case and discussed with the PI and the sponsor.
- Patients with a response (no marrow evidence of leukemia) and pre-cycle counts of neutrophils  $<1 \times 10^9/L$  and platelets  $<50 \times 10^9/L$  may be continued regardless of neutrophil and platelet count with supportive care as needed. Dose-interruptions in these patients should be considered on an individual case and discussed with the PI and the sponsor.
- Investigators should, whenever possible, determine which medication is causing the toxicity and interrupt or dose reduce selinexor and/or sorafenib, as applicable.

### 5.2.2 Selinexor and sorafenib dose adjustments for non-hematologic drug-related AEs

Investigators should, whenever possible, determine which medication is causing the toxicity and interrupt or dose reduce selinexor and/or interrupt sorafenib, as applicable. Thus, if dose level 0 is established as the MTD, one and two dose level reductions of selinexor will be selinexor 60 mg twice weekly and selinexor 40 mg twice weekly, respectively. If the MTD is below dose level 0 further dose reduction levels of selinexor will be defined before moving to the phase II portion of the study. Dose reductions of sorafenib will be as follows: Starting dose = sorafenib 400 mg BID, -1 dose level = 400 mg in the AM and 200 mg in the PM, -2 dose level = 200 mg BID, -3 dose level = 200 mg Qday. The sorafenib dose will not be reduced beyond 200 mg Qday.

**Table 4 Dose adjustments for non-hematologic drug-related AEs, clinically significant in the opinion of the investigator**

Grade	Occurrence	Dose modification
1 or 2	Any time	No dose reduction.
3  (Persistent grade 2: Consider	1st and 2nd time	Hold selinexor and/or sorafenib. Resume selinexor and/or sorafenib at prior dose if recovery to $\leq$ Grade 1 or baseline occurs within 14 days. If toxicity persists for 15-28 days, hold therapy and resume at ONE dose level below current dose for selinexor OR sorafenib

similar dose adjustments if persistent and not responding to optimal management in the opinion of PI and treating physician)		OR both based on which medication is likely causing the toxicity ONLY after recovery of toxicity to $\leq$ Grade 2. Dose re-escalation to prior dose of selinexor OR sorafenib OR both is permitted if tolerated and no recurrent Grade 3 or 4 toxicities occur over 4 weeks while on the lower dose level.
	3 rd and 4th time	Hold selinexor and/or sorafenib. Follow until toxicity $\leq$ Grade 2. Resume at TWO dose level below current dose for selinexor OR sorafenib OR both based on which medication is likely causing the toxicity ONLY after recovery of toxicity to $\leq$ Grade 2. Dose re-escalation by one dose level every 4 weeks of selinexor OR sorafenib OR both is permitted if tolerated and no recurrent Grade 3 or 4 toxicities occur over the 4 weeks while on the lower dose level.
	5th time	Stop selinexor and sorafenib and discontinue patient. (For patients with clinical benefit/response from the combination we will consider continuation if toxicities resolve to $\leq$ grade 1 and with proper dose adjustments after consultation with the PI and the sponsor)
4	Any time	Stop selinexor and sorafenib and discontinue patient. (For patients with clinical benefit/response from the combination we will consider continuation if toxicities resolve to $\leq$ grade 1 and with proper dose adjustments after consultation with the PI and the sponsor)

- If the criteria to resume treatment are met, the subject should restart treatment at the next scheduled time point per protocol. However, if the treatment is delayed past the next scheduled time point per protocol, the next scheduled time point will be delayed until dosing resumes.
- Patients in whom the toxicity occurs or persists beyond the planned completion of drug administration for the cycle will have the dose reductions for either selinexor or sorafenib or both agents (based on attribution of the specific toxicity to selinexor or sorafenib or both) implemented in subsequent cycles provided the toxicity has resolved as specified in table 4 above.
- These general guidelines constitute guidance to the Investigator and may be supplemented by discussions with the Medical Monitor representing the Sponsor in specific cases.
- Guidelines for dose adjustment for toxicities that are likely related to selinexor are given below:

**Table 5 – Specific supportive Care and Dose Adjustment Guidelines for Selinexor-Related Toxicities**

Toxicity and Intensity	Supportive treatment	Selinexor Dose Modification	
Fatigue (common)			
Grade 1	Rule out other causes of fatigue. Consider addition of 4-8 mg dexamethasone or equivalent on the day after selinexor. Insure adequate caloric intake and assess volume status.	Maintain dose.	
Grade 2	Rule out other causes of fatigue. Consider addition of 4-8 mg dexamethasone or equivalent on the day after selinexor. Insure adequate caloric intake and assess volume status. For additional support see NCCN guidelines.	Maintain dose. Consult medical monitor for additional option such as temporary dose reduction or short dose interruptions.	
Grade 3	See guidelines for Grade 2 fatigue	Interrupt selinexor dosing until resolved to Grade $\leq$ 2, For first occurrence of Grade 3, if adequate supportive care resulted in fatigue improving to Grade $\leq$ 1 within 7 days, restart selinexor at current dose. Otherwise, restart selinexor at one dose level below (Table 3).	
Anorexia or Weight loss			

Toxicity and Intensity	Supportive treatment	Selinexor Dose Modification	
Grade 1	
Rule out other causes of anorexia.
 
Assess dietary options (e.g., try a variety of other foods).
 
Add high-calorie supplements (e.g., Ensure®).
 
Consider addition of 4-8 mg dexamethasone or equivalent on the day after selinexor.
	Maintain dose.	
Grade 2	
Rule out other causes of anorexia.
 
Assess dietary options (e.g., try a variety of other foods).
 
Add high-calorie supplements (e.g., Ensure®).
 
Consider addition of 4-8 mg dexamethasone or equivalent on the day after selinexor.
 
Consider megestrol acetate 80-400 mg daily.
 
Consider anabolic steroids such as oxandrolone, or dronabinol (Marinol®) or other cannabinoid, mainly for patients who can't tolerate steroids or at high risk to progress.
 
For additional supportive care see NCCN guidelinesb
	Selinexor may be skipped intermittently while supportive medications are instituted, usually for <1 week.	
Grade 3	See guidelines for Grade 2 anorexia.	
Interrupt dosing with selinexor.
 
Restart selinexor at 1 dose level reduction (Table 3) once anorexia resolves to Grade <math>\leq 2</math> and patient is clinically stable.
	

Toxicity and Intensity	Supportive treatment	Selinexor Dose Modification	
Grade 4 (anorexia only)	See guidelines for Grade 2 anorexia.	Stop dosing of selinexor. Restart selinexor at 1 dose level reduction (Table 3) only if anorexia resolves to Grade $\leq$ 2, patient is clinically stable other contributing factors have been addressed.	
Nausea/ - acute (common)			
Grade 1	Insure adequate caloric intake and assess volume status. Consider alternate 5-HT3 antagonists and/or D2 antagonists as needed. Consider addition of NK1 antagonists. Consider addition of 4-8 mg dexamethasone or equivalent on the day after selinexor.	Maintain dose.	
Grade 2	See guidelines for Grade 1 nausea.  For additional options see NCCN guidelines for antiemesis c	Selinexor may be skipped intermittently while supportive medications are instituted, usually for <1 week.	

Toxicity and Intensity	Supportive treatment	Selinexor Dose Modification	
Grade 3	
See guidelines for Grade 1 nausea
 
For additional options see NCCN guidelines for antiemesisc
	
Interrupt selinexor dosing until resolved to Grade <math>\leq 2</math>, For first occurrence of Grade 3, if adequate supportive care resulted in nausea improving to Grade <math>\leq 1</math> within 3 days, restart selinexor at current dose.
 
Otherwise, restart selinexor at one dose level below (Table 3). If nausea stabilizes for at least 4 weeks at Grade <math>\leq 1</math>, then original dose of selinexor may be resumed.
	
Hyponatremia (common)			
Grade 1 (sodium levels $<$ Normal to 130 nM)	
Be certain sodium level is corrected for hyperglycemia (serum glucose <math>>150</math>mmol/L). Rule out other causes of low sodium (e.g., cardiac, hepatic, adrenal, renal and thyroid diseases, SIADH, Fanconi Syndrome, hyperglycemia, diuretic use).
 
Consider salt supplementation one – two times per day.
	Maintain dose.	

Toxicity and Intensity	Supportive treatment	Selinexor Dose Modification	
Grade 3 (sodium levels 126-129nM) without Symptoms	Be certain sodium level is corrected for hyperglycemia (serum glucose >150mmol/L). Rule out other causes of low sodium (e.g., cardiac, hepatic, adrenal, renal and thyroid diseases, SIADH, Fanconi Syndrome, hyperglycemia, diuretic use). Initiate salt supplementation two-three times per day.	Hold selinexor until Grade $\leq 1$ ( $\geq 130$ nM), restart on the same dose level.	
Grade 3 (120-125 nM) or Grade 4 or any Grade 3 with Symptoms	Correct sodium as per institutional guideline Initiate salt supplementation two-three times per day.	Hold selinexor until resolved to Grade $\leq 1$ ( $\geq 130$ nM) then reduce selinexor dose by 1 level (Table 3). For Grade 3 hyponatremia, if serum sodium stabilizes to grade $\leq 1$ for at least 4 weeks, then original dose of selinexor may be resumed.	
Diarrhea (common)			
Grade 1+2	Diet recommendation as per guidelines (Benson, 2004) d . Institute standard anti-diarrheal therapy. After the first occurrence of diarrhea, loperamide 2 mg should be considered prophylactically approximately 1-2 hours before the administration of selinexor and repeated every 4 hours for the first 12 hours.	For Grade 2 only, reduce selinexor one dose level (Table 3) until resolved to $\leq$ Grade 1, then re-start at the current dose level.	

Toxicity and Intensity	Supportive treatment	Selinexor Dose Modification	
Grade 3	
Institute IV fluids                      Diet recommendation as per guidelines (Benson, 2004)d.
 
Institute standard anti-diarrheal therapy.
 
Once the symptoms resolve to <math>\leq</math>Grade 1, loperamide 2 mg should be considered prophylactically approximately 1-2 hours before the administration of selinexor and repeated every 4 hours for the first 12 hours.
	
Delay selinexor until resolved to <math>\leq</math> Grade 1, then reduce selinexor dose by one dose level (Table 3).
 
If diarrhea stabilizes for at least 4 weeks at Grade <math>\leq</math>1, then original dose of selinexor may be resumed.
	
Grade 4	
Rule out other causes of diarrhea, including infectious agents. In case of opportunistic infection, withdraw all steroids (with tapering if medically appropriate) until culture is negative. Follow institutional guidelines for Grade 4 diarrhea.
	
Delay selinexor until resolved to <math>\leq</math> Grade 1, then reduce selinexor dose by one dose level (Table 3).
	
Other selinexor-related adverse events*			
Grade 1 or 2	
Initiate standard supportive care and follow institutional guidelines.
	
Maintain dose.
	
Grade 3	
Initiate standard supportive care and follow institutional guidelines.
	
Delay dose until resolved to Grade <math>\leq</math> 1 or baseline, then reduce by one dose level (Table 3).
	
Grade 4	
Initiate standard supportive care and follow institutional guidelines.
	
Delay dose until resolved to Grade <math>\leq</math>1 or baseline, then reduce by two dose levels (Table 3).
	

Toxicity and Intensity	Supportive treatment	Selinexor Dose Modification	
All dose modifications should be based on the worst preceding toxicity.			
* Isolated values of $\geq$ Grade 3 alkaline phosphatase values will NOT require dose interruption. Determination of liver vs. bone etiology should be made, and evaluation of gamma-glutamyl transferase (GGT), 5'-nucleotidase (5'NT), or other liver enzymes should be performed.			
a National Comprehensive Cancer Network® . NCCN Clinical Practice Guidelines in Oncology (NCCN Guidelines®): Fatigue. Available at http://www.nccn.org/professionals/physician_gls/pdf/fatigue.pdf			
b National Comprehensive Cancer Network® . NCCN Clinical Practice Guidelines in Oncology (NCCN Guidelines®): Palliative Care, version 1.2014. Fort Washington, NY. April 2014. Available at: http://www.lls.org/content/nationalcontent/resourcecenter/freeeducationmaterials/generalcancer/pdf/facts.pdf .			
c National Comprehensive Cancer Network® . NCCN Clinical Practice Guidelines in Oncology (NCCN Guidelines®): Antiemesis, version 2.2014. Fort Washington, NY. April 2014. Available at: http://www.nccn.org/professionals/physician_gls/PDF/antiemesis.pdf .			
d Benson AB, Ajani JA, Catalano RB, et al. Recommended guidelines for the treatment of cancer treatment-induced diarrhea. J Clin Onc 2004; 22:2918.			

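### Two hyponatremia rows of Table 5 tie the sodium correction to serum glucose above 150 mmol/L, a unit that cannot be meant (probably mg/dL); as a minor point, the section 3.4 footnote prints 1.6 beside a formula worth 2.4 per 100 mg/dL

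*Combined protocol and SAP*

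**What the plan says.** Table 5 (selinexor-related toxicities) has three hyponatremia rows. The Grade 1 row and the asymptomatic 126-129 row carry the same instruction in the supportive-treatment column: "Be certain sodium level is corrected for hyperglycemia (serum glucose >150 mmol/L". The next sentence in each cell is "Rule out other causes of low sodium (e.g., cardiac, hepatic, adrenal, renal and thyroid diseases, SIADH, Fanconi Syndrome, hyperglycemia, diuretic use", with no glucose level attached.

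The Grade 1 row keeps the dose unchanged. The row headed "Grade 3 (sodium levels 126-129nM) without Symptoms" holds selinexor until sodium is at least 130 and then says "restart on the same dose level". The third row (120-125, Grade 4, or symptomatic Grade 3) prints no glucose threshold.

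The text after Table 4 in section 5.2.2, which introduces Table 5, gives the status of these rules: "These general guidelines constitute guidance to the Investigator and may be supplemented by discussions with the Medical Monitor".

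Section 3.4 makes sodium below 125 mmol/L a DLT, except for asymptomatic translational hyponatremia due to hyperglycemia, for which it says "see footnote below for calculation". The footnote describes sodium as "declining 1.6 mEq/L for every 100 mg/dL (5.55 mmol/L" of glucose above normal. It then gives one labelled formula for corrected sodium, beginning "Measured sodium + 0.024", in which the coefficient multiplies serum glucose minus 100. No unit is printed for glucose in the formula.

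**The concern.** A sodium value lowered only by high glucose should not lead to withholding selinexor, and the correction instruction is there to prevent that. If its trigger is set at a glucose that patients will not reach, the instruction does nothing on a literal reading. A patient with moderate hyperglycemia and a measured sodium of 126-129 could then be held without the correction being made. The unit looked wrong at once, because section 3.4 works in mg/dL and gives its own conversion to mmol/L.

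The section 3.4 footnote raises a smaller question of consistency. Its descriptive sentence and its formula imply different corrections for the same glucose, and the DLT exception refers the reader to that footnote.

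**Working it through.** The threshold is stated and not derived from other inputs, so there is no calculation in the plan to reproduce. The check is whether it agrees with the protocol's own conversion and formula.

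**Inputs**
- Threshold: serum glucose above 150 mmol/L (Table 5, two rows).
- Conversion: 100 mg/dL = 5.55 mmol/L (section 3.4 footnote).
- Formula: corrected Na = measured Na + 0.024 × (glucose − 100) (section 3.4 footnote). The constant 100 makes sense only in mg/dL.
- Descriptive slope: 1.6 mEq/L per 100 mg/dL (same footnote).
- Release from the 126-129 hold: sodium at least 130 (Table 5).

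**1. The printed threshold in mg/dL**

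150 × 100 / 5.55 = 2,702.7 mg/dL.

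**2. What the formula does at that glucose**

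0.024 × (2,702.7 − 100) = 62.5 mmol/L. A measured sodium of 126 would correct to 126 + 62.5 = 188.5. The protocol's own figures therefore rule out the printed unit.

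**3. The probable threshold**

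150 mg/dL × 5.55 / 100 = 8.3 mmol/L. The formula adds 0.024 × (150 − 100) = 1.2 mmol/L, a plausible size for the point at which correction begins to matter.

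**4. The two slopes in section 3.4**

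Formula: 0.024 × 100 = 2.4 per 100 mg/dL. Descriptive sentence: 1.6 per 100 mg/dL. They do not match.

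**5. What the correction could change in the 126-129 row**

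Table 5 names no formula, so both slopes are shown, with unrounded results, at glucose 200 mg/dL:

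| Measured Na | Slope 1.6 | Slope 2.4 |
|---|---|---|
| 126 | 127.6 | 128.4 |
| 129 | 130.6 | 131.4 |

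A measured 129 would leave the hold row under either slope, and a measured 126 would stay in it. This assumes that the corrected value decides the row. Table 5 implies that but does not state it.

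**6. Why the formula should carry its unit**

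Glucose 200 mg/dL is 200 × 5.55 / 100 = 11.1 mmol/L. A reader who carried over Table 5's mmol/L would compute 0.024 × (11.1 − 100) = −2.1, a correction in the wrong direction.

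**The case against.** The strongest reply is that nobody would be misled. The trial runs at a single institution, section 3.4 uses mg/dL, and the same Table 5 rows print sodium in nM, another evident typing slip. The faulty unit sits in a parenthesis, while the instruction itself, to correct sodium for hyperglycemia, is clear. The next sentence asks for hyperglycemia to be ruled out at any level. Table 5 is for toxicities likely related to selinexor, so low sodium explained by glucose arguably falls outside it. Section 5.2.4.4 allows other modifications after discussion. The Grade 1 row involves no dose change, and the 126-129 hold errs on the safe side and ends at the same dose.

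Most of this stands, and it limits the consequence. A reader might infer from the printed unit that the instruction is unusable or that the correction would never be made. The documents do not support that, given the threshold-free sentence in the same cell and the guidance status of the rules. The reply does not make the printed threshold right. It appears identically in two rows that investigators are meant to use, one of them beside a hold of study drug.

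On the footnote, the reply is that 1.6 is background physiology and the only labelled formula uses 0.024. That also stands: a site that uses the formula is unaffected.

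**Conclusion.** The point holds as a minor correction. The glucose unit in two Table 5 rows is wrong as printed, by the protocol's own arithmetic. That mg/dL was meant is an inference from section 3.4, and the investigator should confirm it. The likely worst effect is an occasional unnecessary temporary hold of selinexor. The documents give no frequency for hyperglycemia or for sodium of 126-129, so how often this could happen cannot be estimated.

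Two stronger conclusions are tempting and not supported:

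- A reader might infer that the 1.6 and 2.4 slopes lead to different DLT calls at identifiable sodium values. Section 3.4 does not say how corrected sodium is rounded, or that reaching 125 after correction is what satisfies the exception. For example, a measured 123 at glucose 200 mg/dL gives 124.6 or 125.4, and both round to 125. The mismatch is real, but the labelled formula is the operative calculation and no particular misclassification is shown.
- A reader might infer that unnecessary holds would make Phase I patients non-evaluable for DLT. Section 5.1.1.5 requires at least 4 selinexor doses in cycle 1, and 6 are scheduled (2 per week for 3 weeks), so a hold would have to cost 3 doses. That is possible, but nothing in the documents shows it to be likely.

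The MTD rule, the CRc endpoint and the Phase II stopping boundaries do not depend on the Table 5 threshold.

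**What to change.** In Table 5 (selinexor-related toxicities), change the glucose unit from mmol/L to mg/dL in the Grade 1 and the asymptomatic 126-129 hyponatremia rows, once the investigator has confirmed the intended value.

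As a minor addition in the section 3.4 footnote, delete the descriptive 1.6 mEq/L per 100 mg/dL or align it with the labelled formula (0.024 per mg/dL, or 2.4 per 100 mg/dL), and print mg/dL as the glucose unit in that formula.

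Both are wording changes. They need no new data and no recalculation, and leave the design unchanged.
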